Title:

Prevention of Musculoskeletal Injuries in Slovenian Armed Forces

NCT 03415464

Unique Protocol ID: 630-1/2016-3

Date: 3rd May 2020

This was a two arm randomized control trial in which soldiers were randomized into control (N=41) and experimental (N=64) group. The sample size calculation was based on an expected difference of 25% in physical ability parameters (continuous variables) between the intervention and control group. Assuming a Type I error (α) = 0.05 and Type II error (β) = 0.20, a minimum of 70 soldiers (35 per study group) was required to detect a significant increase of physical abilities. Due to an expected “dropout/noncompliance rate” of 5% the total calculated number was 75 soldiers. Prior and following the intervention both groups underwent physical fitness testing. The effect of intervention was evaluated through the change in performance on those tests. Injury occurrence was followed for the period of one year from February 2017 to February 2018. Injuries were prospectively registered on a weekly basis.

Physical fitness testing

The PPT testing was performed in the gym of the SAF military post. All tests were conducted between 8 AM and 12 PM, and the actual arrival to the testing location was adjusted to daily routine and tasks of the soldiers according to a testing list provided by a commanding officer. Each testing group had 18 members, and they arrived at the gym 15 minutes before testing. The testing procedure was then explained and briefly demonstrated by an independent military member that was not participating in the study. After the introduction all soldiers had 10 minutes to warm-up. The test battery started with either a jump test or pull-ups. The testing battery did not start with a single leg bridge test (SLBT) as this could potentially influence subjects' jumping or balance capacity. It was therefore performed as the third test together with a plank test (Figure 1). During the testing, all subjects were in combat SAF uniforms and were wearing standard SAF military boots. Where needed, body armors and helmets were used (total weight of 8.4 kgs). The testing battery is depicted in Figure 2.

Countermovement Jump (CMJ) Testing. To measure the magnitude and direction of forces during CMJ jumps, 2 Kistler force platforms (Kistler 9286AA; Kistler Instrument Corp, Winterthur, Switzerland) with custom-made ARS software (S2P, Science to Practice, Ltd., Ljubljana, Slovenia) were set up in parallel, so that the subjects could place each foot on 1 platform while performing a jump. The subjects started a test from an upright standing position (Figure 2A) with hands held on hips, making a preliminary downward movement by flexing at the knees and hips, then immediately extending knees and hips again to jump vertically up off the ground. For the purposes of the current study, only CMJ height in centimeters (calculated from flight time) was used as an outcome measure. The CMJ test was performed in uniform and boots, and then, the same procedure was repeated with soldiers wearing body armor and a helmet (loaded CMJ; Figure 2B). Under each testing condition, a subject had 2 jump trials, and the repetition with the highest jump was used for further analysis.

Single Leg Bridge Test. The SLBT is a simple field test for hamstring function where soldiers initially lie down on the ground with 1 heel on a box 60 cm high (Figure 2E) as previously proposed (8). Subjects were instructed to push down through the heel to lift their bottom off the ground while holding their arms crossed over the chest. Consistent verbal coaching was provided throughout the procedure to ensure that the correct technique was maintained. Repetition was considered regular when the subject has touched the ground and has then extended his hip to 0° without resting on the ground. It was not allowed to use a non-testing leg to gain momentum by, e.g., by swinging that leg. The test was terminated when the technique became irregular or a subject could not proceed with the test due to fatigue. After a short break, the test was repeated for the opposite leg. The initial testing leg was randomly chosen for each subject. The number of successful repetitions for each leg was used as the outcome measure for further analysis. This testing protocol has been previously shown good to have excellent reproducibility with intra-rater intraclass correlation coefficient (ICC) values in the range of 0.77–0.89 and inter-rater ICC values in the range of 0.89–0.91 (8).

Loaded Prone Plank Test. For the prone plank test, subjects maintained a prone position in which the body mass was supported by the toes and forearms (Figure 2F). The test was performed in a full army uniform while wearing body armor and a helmet. Subjects were instructed to maintain a neutral position of the spine and pelvis and to breathe normally during testing. Elbows were directly below the shoulders, and forearms and fingers were extending forward, while the feet were kept shoulder-width apart. To assist them in achieving a rigid neutral position, a wooden stick was used to help the align spine and

pelvis. Although we are aware that oscillation of the wooden stick may vary according to the anthropometry of the subject, we have successfully implemented the test as this was only an additional

[figure not shown]
tool for subjects to better understand the required testing position. Each test was terminated when the subject was unable to maintain their posture or their pelvis moved up or down 5 or more centimeters. Each holding time was recorded using a stopwatch. The holding time (seconds) of the prone plank test was used for further analysis. The reproducibility of this test has been confirmed in previous studies (30) with reported ICC values of 0.99 (95% confidence interval 0.98–0.99) and (coefficient of variation [CV]) 2.0 6 1.56%.

Pull-ups. The starting position for pull-ups was with arms fully extended and locked in elbows (Figure 2C), with an overhand grip, the body motionless, and feet off the floor. From this starting position, the subject was instructed to bend and cross-over the knees backward and then to pull-up over the bar until the chin has cleared the top of the bar without any excessive body motion. The body was then lowered until arms are again fully extended or locked out. One complete pull-up was counted when the subject's arms were locked out. This procedure is repeated at the subject's own pace (rest between repetitions was allowed only in the full hang position) until the subject could no longer complete a full pull-up. The number of successful repetitions was used as the performance measure in this task.

Stork Balance Stand Test. The stork balance stand test is a single leg balance test with eyes closed. The testing position is single leg stance with hands on the hips, where the non-supporting foot is held against the inside knee of the supporting leg (Figure 2D). The subject is instructed to close their eyes, raise the heel off the floor, and balance on the support base of the anterior foot. The stopwatch was started as the heel was raised from the floor. The stopwatch was stopped if any of the following occurred: the hand(s) came off the hips, the supporting foot swiveled or moved (hops) in any direction, the non-supporting foot lost contact with the knee, or the heel of the supporting foot touched the floor. The total time in seconds for each leg was recorded.

Intervention

Experimental group was training according to specific 12 week functional training program (6 exercises, 2 times a week, progressive, functional), while control group trained according to standard SAF training routine. Standard SAF routine considers five 1-hour training sessions per week. In experimental group only 2/5 training sessions were modified.

Statistical Analyses

Mean values and SDs were calculated for all tests. The normality of data was checked using the Shapiro-Wilk test. For the MANUAL test, percentile ranks were reported. Multivariate analysis of covariance with post hoc Bonferroni correction for multiple comparisons was used to evaluate functional performance

differences in relation to APFT mark (range 2–5) while controlling for age and body mass. Levene's test of equality of error variances was used to check that the error variance is equal across groups. Chi square test was used to compare injury rates in experimental and control group. A significance level of 0.05 was used for each tes

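### Post hoc APFT-mark comparisons: single-step Bonferroni is valid, but Holm's step-down version never rejects less at the same family-wise bound

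*Combined protocol and SAP*

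**What the plan says.** The Statistical Analyses section of the combined protocol and SAP gives one model for the fitness tests: "Multivariate analysis of covariance with post hoc Bonferroni correction for multiple comparisons". It is used to look at functional performance "differences in relation to APFT mark (range 2–5) while controlling for age and body mass". On the level, the section says "A significance level of 0.05 was used for each tes", where the text breaks off. It does not give the number of post hoc comparisons. It also does not say whether the correction runs over pairs of marks within one fitness test or across the tests as well, or what power these comparisons have.

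The sample size in the opening design paragraph concerns something else, an "expected difference of 25% in physical ability parameters (continuous variables) between the intervention and control group".

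**The concern.** Single-step Bonferroni holds every comparison to the level set by the full number of comparisons, even after some pairs have been declared different. That is stricter than the family-wise guarantee requires. Holm's procedure orders the same p-values and relaxes the threshold after each rejection, and it controls family-wise error under any dependence among the tests. Whatever the data, it rejects at least the pairs that Bonferroni rejects.

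What is at stake is power to say which marks differ. Distant marks are easy to separate under either rule. Neighbouring marks are the hard cases, and most of the avoidable loss falls on them.

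**Working it through.** **The plan's own figure.** No power or sample size is stated for the APFT-mark comparisons, so there is no figure to reproduce for them. The stated sample size is for the two arms. "Assuming a Type I error (α) = 0.05 and Type II error (β) = 0.20", two-sided (sidedness is not given), 35 per group corresponds to a standardized difference of (1.960 + 0.842) × √(2/35) = 0.67. A 25% difference then implies an SD of about 25/0.67 = 37% of the mean. No SD is given, so this cannot be confirmed. For dropout, 70/0.95 = 73.7, so 74 against the stated 75, which is close enough. None of this bears on differences between marks.

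**Inputs.**
- From the documents: Bonferroni; marks 2 to 5; level 0.05; 41 + 64 = 105 soldiers.
- Inferred: all four marks occur, giving 4 × 3/2 = 6 pairs; the family is those six pairs within one fitness test; tests are two-sided.
- Assumed: soldiers per mark, either 26/26/26/27 or 10/25/40/30; equal steps between successive marks, in SD units; one outcome at a time, with error degrees of freedom 105 − 4 marks − 2 covariates = 99.

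**Thresholds.** Bonferroni uses 0.05/6 = 0.00833 for all six pairs. Holm uses 0.05/6, 0.05/5, …, 0.05/1 on the ordered p-values, stopping at the first failure: 0.00833, 0.0100, 0.0125, 0.0167, 0.025, 0.05. The first step is the same, so any gain comes only after a first rejection.

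**Power.** Simulation, 40,000 data sets per scenario (Monte Carlo standard error at most √(0.25/40,000) = 0.25 points), near-equal mark sizes:

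| Step per mark | Average over true pairs, Bonferroni → Holm | Neighbouring marks, Bonferroni → Holm |
|---|---|---|
| 0.25 SD | 17.2% → 18.7% | not tabulated |
| 0.4 SD | 40.9% → 45.1% | 11.3% → 15.9% |
| 0.6 SD | 63.6% → 71.6% | 30.6% → 45.2% |
| 0.8 SD | 79.0% → 89.2% | 58.1% → 78.4% |

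With sizes 10/25/40/30 the average gain is 3.9, 8.1 and 9.2 points at 0.4, 0.6 and 0.8 SD. Across both sets of sizes it is 1.1 to 1.5 points at 0.25 SD.

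**At least one true difference found.** The two rules agree: 60.1% for both at 0.25 SD and 96.7% for both at 0.4 SD (near-equal sizes).

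**Error control.** With no true differences, family-wise error is 4.3% for both rules (near-equal sizes) and 4.0% for both (unequal sizes). With only one mark differing, by 0.8 SD, Holm's error is 3.4% against 2.3% for Bonferroni, still below 5%. In no simulated data set did Bonferroni reject a pair that Holm did not.

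**The case against.** The strongest reply is that nothing here is an error. Bonferroni is valid and conservative, and it comes with simple simultaneous intervals. A reader might infer that the plan's error control is faulty. The documents do not support that: the only loss is power.

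Second, other methods are available. Shaffer's step-down procedure for all pairs among four means improves on Holm in turn (47.0% against 45.0% average power at 0.4 SD), and Tukey's method gives intervals and a better chance of at least one finding (63.5% against 60.1% at 0.25 SD). This stands as a reason not to treat Holm as the only choice. It does not alter the fact that Holm dominates Bonferroni.

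Third, the size of the gain rests on assumptions. The larger gains need 0.6 to 0.8 SD per mark, which is 3 × 0.6 = 1.8 to 3 × 0.8 = 2.4 SD between marks 2 and 5 after adjustment for age and body mass. The calculation also treats one outcome at a time and does not model the multivariate test. This stands in full.

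Fourth, the documents state neither six pairs nor a family for each test. If Bonferroni was applied across tests as well, applying Holm only within each test would narrow the family and loosen error control. This also stands, so the replacement must cover the same family.

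Fifth, the text is in the past tense, dated May 2020, and injury follow-up ended in February 2018. If the results are known, moving to a rule that can only add significant pairs is a post hoc change. That stands as a condition on the fix.

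**Conclusion.** The point holds as a cheap improvement, not as a defect. For the APFT-mark comparisons, Holm is at least as good a testing rule as Bonferroni in every data set, with the same 5% family-wise bound. If all four marks occur and the family is six pairs within one test, the average gain per true pair is about 1 point at 0.25 SD per mark, 4 points at 0.4 SD, and 8 to 10 points at 0.6 to 0.8 SD, under the assumed mark sizes. The gain for finding at least one difference is nil.

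Because this is the only model given for the fitness scores, a reader might infer that the trial's main comparison loses power. The documents do not support that. The opening design paragraph judges the intervention by change in test performance between two arms. Two arms give one pair per test, where the two rules coincide over pairs. The model described has APFT mark as its factor and does not mention the randomized arm. That is a separate and larger matter, which a change to Holm would not mend.

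**What to change.** In the Statistical Analyses section, replace the Bonferroni wording with: *pairwise comparisons of adjusted means between APFT marks, with Holm step-down adjustment over [the stated family]*. The family should be the one to which Bonferroni was applied. State explicitly whether that is the pairs within each fitness test or also spans the tests, and how many comparisons it contains. Report Holm-adjusted p-values.

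The work is one sentence and a re-ordering of unadjusted p-values from the same model, with no refitting and no new data. There are two costs:
- Holm has no equally simple simultaneous confidence intervals. If Bonferroni intervals are kept beside Holm p-values, a pair declared different can have an interval that includes zero, and the report should say so.
- If results are already known, the Holm analysis must be labelled post hoc, with the Bonferroni results shown beside it.

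### The only fitness model in the analysis section has APFT mark as its factor and no term for randomised arm, so it cannot estimate the intervention effect on which the trial was sized

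*Combined protocol and SAP*

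**What the plan says.** The opening design paragraph describes a two-arm randomised trial with 41 control and 64 experimental soldiers. On fitness it says: "Prior and following the intervention both groups underwent physical fitness testing". It then says how the intervention is judged: "The effect of intervention was evaluated through the change in performance on those tests". The sample size rests on "an expected difference of 25% in physical ability parameters (continuous variables) between the intervention and control group", with α = 0.05 and β = 0.20, giving 35 per group.

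The Statistical Analyses section gives one inferential analysis for fitness: "Multivariate analysis of covariance with post hoc Bonferroni correction for multiple comparisons was used to evaluate functional performance", and the sentence continues "differences in relation to APFT mark (range 2–5) while controlling for age and body mass". The other items in the section are:

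- means and SDs, and a Shapiro-Wilk check;
- a reporting rule for a further test ("For the MANUAL test, percentile ranks were reported");
- Levene's test;
- the one test that names the arms ("Chi square test was used to compare injury rates in experimental and control group");
- the significance level, which ends mid-word in the extracted text ("A significance level of 0.05 was used for each tes").

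Neither the APFT mark nor the MANUAL test is described elsewhere in the document.

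**The concern.** The design paragraph and the analysis section answer different questions. The first asks whether the modified training changed fitness relative to standard training. The model in the second asks whether soldiers with different APFT marks perform differently, given age and body mass. APFT mark was not randomised, so its contrasts compare soldiers who may differ in many other ways, and none of them estimates the training effect.

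What is at stake is the comparison that justified the sample size. A reader who follows the analysis section as it stands obtains no between-arm difference, confidence interval or p-value for any fitness test.

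The multiplicity statement has the same problem. The Bonferroni correction is attached to the APFT-mark model and does not say how arm comparisons over several outcomes would be handled.

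**Working it through.** **1. Terms in the model against terms needed.**

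| Needed for the stated effect | In the stated fitness model |
|---|---|
| Factor: experimental vs control | Factor: APFT mark, 2 to 5 |
| Change, or post-intervention value given pre-intervention value | Outcome time point not stated; no pre-intervention covariate |
| Optional covariates | Age, body mass |

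Even if the outcomes are change scores, a model without an arm factor does not estimate the arm difference.

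**2. Outcomes affected.** The test descriptions give CMJ, loaded CMJ, single leg bridge (2 legs), loaded plank, pull-ups and stork stand (2 legs): 1 + 1 + 2 + 1 + 1 + 2 = 8, or 6 with legs combined. The number given a between-arm estimate is 0. The undescribed MANUAL test is not counted.

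**3. What the Bonferroni correction covers.** Four marks give 4 × 3 / 2 = 6 pairs. Two arms give 1. A correction over pairs of marks leaves the single arm contrast untouched and does not address multiplicity across outcomes. With 8 independent arm tests at 0.05 each, the chance of at least one false positive is 1 − 0.95^8 = 34% (6 tests: 1 − 0.95^6 = 26%). It is lower if the tests are positively correlated.

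**4. The plan's own sample size.** The 35 per group cannot be reproduced directly, because the 25% difference comes without an SD and sidedness is not stated. Solving backwards (two-sample t, 35 per group, α = 0.05, power 0.80) gives a standardised difference of d = 0.679 two-sided or 0.600 one-sided. The two-sided value corresponds to an SD of 25 / 0.679 = 37% of the mean. The dropout step gives 70 / 0.95 = 73.7, so 74 against the stated 75; this does not affect the point.

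**5. What an arm model could deliver with 41 and 64.** Assumptions: all 105 analysed, two-sided test, age and body mass explaining no variance. In SD units SE = √[(1 − r²)(1/41 + 1/64)], where r is the assumed pre-post correlation. The degrees of freedom are 103 minus the number of covariates (2 without the pre-intervention value, 3 with it). Power is from the noncentral t.

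| | No pre-intervention value | r = 0.5 | r = 0.7 |
|---|---|---|---|
| SE | 0.200 | 0.173 | 0.143 |
| Degrees of freedom | 101 | 100 | 100 |
| Detectable d, 80% power, α = 0.05 | 0.566 | 0.490 | 0.404 |
| 95% CI half-width | 0.397 | 0.344 | 0.283 |
| Power at d = 0.679, α = 0.05 | 92% | 97% | over 99% |
| Power at d = 0.600, α = 0.05 | 84% | 93% | 99% |
| Power at d = 0.679, α = 0.05/8 = 0.00625 | 72% | 87% | 97% |
| Power at d = 0.600, α = 0.00625 | 58% | 75% | 92% |

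**6. Illustration with assumed data.** In 1000 simulated trials per setting, baseline fitness rose with APFT mark and post-intervention fitness depended on baseline plus an arm effect of 0.67 SD or none. An ANCOVA on arm, pre-intervention value, age and body mass rejected in 98% of runs with the effect and 5% without. The F test for APFT mark rejected in 33% and 35%, so it did not respond to the arm effect. The percentages depend on the assumed inputs; the lack of response follows from the model having no arm term.

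**The case against.** The strongest objections do not claim that the model contains an arm term.

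- **The text is cut mid-word**, in the section where an arm model would stand. This is fair, and it is why the point is limited to what is described. The cut falls in the significance-level sentence, after the fitness model is complete, so that model would need reconciling with the design paragraph in any case.
- **The outcomes might be change scores.** The section does not say. It would be too strong to assert that change was not analysed. Without an arm factor, though, change scores still give no arm effect.
- **Levene's test refers to groups, which may mean arms.** Even so, it is an assumption check and not an effect estimate.
- **Injuries, the subject of the title, do get an arm comparison, and no primary outcome is named.** This is true, but the sample size was built on fitness.
- **The power figures concern a model that is not in the document.** They do not measure the defect; they show only whether an arm analysis would be informative. The reassurance holds at 0.05 per test and not generally. At 0.00625, power falls below 80% in three of the six scenarios. If the SD were 50% of the mean, so that d = 0.50, power without the pre-intervention value would be 70% even at 0.05. Any dropout lowers it further.
- **Comparing change scores between arms would also fit the design paragraph.** It would. With the pre-intervention value as a covariate, the estimated arm effect is the same whether post-intervention value or change is the outcome.

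**Conclusion.** The concern holds and must be fixed. As written, the analysis section gives a between-arm estimate for 0 of the 8 described fitness outcomes (0 of 6 with legs combined), although that difference defines the intervention effect and sized the trial. This conclusion comes from reading the model terms and needs no numerical assumption. The document shows that the arm analysis is not described; it does not show that none was done.

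At 0.05 per test, with all 105 soldiers analysed and the planning effect implied by 35 per group, the trial is large enough for the comparison. What is missing is the model. That adequacy is conditional on the assumptions listed and weakens if the arm tests are corrected across outcomes.

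**What to change.** In the Statistical Analyses section:

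- If an arm-based fitness model was run, state it: factor, outcome time point and covariates.
- If not, fit one with randomised arm as the factor, post-intervention value as the outcome, and pre-intervention value, age and body mass as covariates, either as a MANCOVA or as one ANCOVA per test.
- Report the adjusted between-arm difference with its 95% CI for every test.
- State whether arm comparisons are each tested at 0.05 or corrected across outcomes. A threshold of 0.05/8 = 0.00625 would be a new rule and not the Bonferroni correction now in the text.
- Keep any APFT-mark analysis separate and descriptive, and define the APFT mark and the MANUAL test.
- Label the arm model post hoc only if it was chosen after the data were seen. The May 2020 document date does not by itself show this.

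The cost is revised wording and, if no arm model exists, a small re-analysis of test data already collected in both groups. The downside is that a model chosen after the data were seen carries less weight than a prespecified one.

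### The only stated model for the fitness scores is by APFT mark, not trial arm, and no primary outcome or multiplicity rule covers an arm comparison of the battery

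*Combined protocol and SAP*

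**What the plan says.** All references are to the combined protocol and SAP.

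- **Opening paragraph.** "The effect of intervention was evaluated through the change in performance on those tests". This refers to the battery as a whole, and no score is named primary. The sample size is likewise based on physical ability parameters in the plural: 35 per arm, alpha 0.05, power 80%, with no SD.
- **Test descriptions.** The jump is scored unloaded, and then "the same procedure was repeated with soldiers wearing body armor and a helmet". For the single leg bridge, "The number of successful repetitions for each leg was used as the outcome measure for further analysis". Plank time and pull-up count give one score each. Stork balance time is recorded for each leg, but is not said to be carried into the analysis.
- **Statistical Analyses, fitness.** The model is given as "Multivariate analysis of covariance with post hoc Bonferroni correction for multiple comparisons was used to evaluate functional performance". The rest of that sentence sets out what is compared and what is adjusted for: "differences in relation to APFT mark (range 2–5) while controlling for age and body mass". The factor is APFT mark; trial arm does not appear.
- **Statistical Analyses, injuries.** "Chi square test was used to compare injury rates in experimental and control group". This is the only test stated to compare the arms.
- **Statistical Analyses, other.** "For the MANUAL test, percentile ranks were reported", although no such test is described elsewhere. The last visible sentence is "A significance level of 0.05 was used for each tes", cut off in mid-word.

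**The concern.** The effect of training is to be read from the fitness battery, yet the model given for the battery answers a different question: how performance differs across APFT marks 2 to 5, adjusted for age and body mass. A reader cannot tell which analysis by arm, on which scores, would count as showing a fitness benefit.

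The Bonferroni step does not fill the gap. As a post hoc step in that model it covers comparisons among marks. With two arms there is only one arm contrast, so there would be nothing of that kind to correct even if the model were rerun by arm.

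What remains is a general level of 0.05 per test and several scores of equal standing. If they were tested separately by arm, one significant score could be reported as the intervention working, with an error risk well above the nominal 5%.

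**Working it through.** **1. The plan's own figures.** The plan states no error rate for the battery, so there is none to reproduce. The nearest figures are in the sample size. Adding 5% dropout to 70 gives 70/0.95 = 73.7, or 74, against the stated 75, which is close enough. The 70 itself cannot be derived without an SD. Working backwards, 35 per arm with 80% power at two-sided 0.05 corresponds to a standardised difference d of about 0.68 by the t distribution. The calculation is for one test at 0.05.

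**2. How many scores.**
- *Eight:* jump, loaded jump, bridge left and right, plank, pull-ups, stork left and right.
- *Six:* stork not analysed, or left and right legs combined.
- *Five:* both, that is jump, loaded jump, combined bridge, plank, pull-ups.
- *Nine:* if the undescribed MANUAL test is one further outcome.

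**3. False-positive chance if each score is tested by arm at two-sided 0.05, with no true effect.** For k independent tests the chance of at least one false positive is 1 − 0.95^k:
- k = 5: 1 − 0.774 = 22.6%
- k = 6: 1 − 0.735 = 26.5%
- k = 8: 1 − 0.663 = 33.7%
- k = 9: 1 − 0.630 = 37.0%

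The scores will be correlated, and the documents give no correlations. For normal test statistics with a common correlation r, the chance is 1 − ∫ φ(u) [Φ((1.96 − √r·u)/√(1−r)) − Φ((−1.96 − √r·u)/√(1−r))]^k du. By numerical integration:

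| Scores | r = 0 | r = 0.5 | r = 0.7 | r = 0.9 |
|---|---|---|---|---|
| 5 | 22.6% | 18.3% | 14.8% | 10.2% |
| 6 | 26.5% | 20.7% | 16.4% | 10.8% |
| 8 | 33.7% | 25.0% | 19.1% | 11.9% |
| 9 | 37.0% | 26.9% | 20.2% | 12.4% |

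Neither end suits this battery. Zero does not fit two legs of one test or two versions of one jump, and 0.9 is extreme across jumping, planking, pull-ups and balance. A paired pattern is more plausible: the two jumps, the two bridge legs and the two stork legs are strongly correlated, and all other pairs less so. By simulation (2 million draws):

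| Pattern (assumed) | Eight | Six, no stork | Six, legs averaged | Five |
|---|---|---|---|---|
| Pairs 0.8, others 0.3 | 27% | 22% | 23% | 20% |
| Pairs 0.9, others 0.5 | 22% | 18% | 19% | 17% |

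**4. Alternatives.** One multivariate test by arm at 0.05 carries about 5%. Holm over eight scores keeps the rate at or below 5% (4.9% if independent). With injuries tested separately at 0.05, the two families together carry at most 0.05 + 0.05 = 10%.

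**5. Cost in power for one score.** This uses the noncentral t with d = 0.679 (back-solved, two-sided, illustrative only). The first Holm step over eight is 0.05/8 = 0.00625. The correlation-aware first-step threshold at correlation 0.7 is 0.0106. Dropout of 5% takes 41 and 64 to 38.95 and 60.8, rounded to 39 and 61.

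| Level | 35/35 | 41/64 | 39/61 |
|---|---|---|---|
| 0.05, one test | 80% | 92% | 91% |
| 0.00625, Holm first step | 51% | 73% | 70% |
| 0.0106, correlation-aware | 59% | 78% | 76% |

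**The case against.** **The inflation rests on an analysis that the plan never states.** This stands. Nothing visible says that the scores were compared between arms one at a time, and the 0.05 sentence may give only the nominal level of each listed procedure. A reader might infer that the plan tests eight scores unadjusted and so runs a 12-34% false-positive risk. The documents do not support that: the range depends both on separate testing and on an assumed common correlation from 0.9 down to 0. It is an illustration, not a property of the plan.

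**The authors' stated approach to several scores is multivariate with Bonferroni.** This counts against assuming that they would run unadjusted tests. It does not close the gap, because the factor is APFT mark.

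**The text is cut off.** An arm analysis or a further error rule could have followed, and the visible text cannot exclude it. A reader might infer that the full plan has no such rule; that cannot be claimed. Still, the cut comes after the methods have been listed, and the mismatch between the stated model and the stated basis for judging the effect lies in text that is complete.

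**Family-wise control over every score is only one choice.** Partly accepted: scores left outside the controlled family can be reported as exploratory estimates.

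**Conclusion.** The point holds for the visible text. The stated fitness model does not compare the randomised arms, its Bonferroni step does not extend to them, and no primary outcome is named, although the intervention is judged on the whole battery. This needs no assumption about correlations or the number of scores.

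The size of the error is conditional. If the scores are compared by arm separately at two-sided 0.05, the chance of at least one false-positive fitness result is about 22-27% for eight scores, 18-23% for six and 17-20% for five under the paired patterns. Over common correlations from 0.9 to 0 the ranges are 12-34%, 11-26% and 10-23%. If one multivariate test by arm was intended, it is about 5%. Confidence is medium because of the cut-off text and the open count of scores. The matter should be put right, but it does not show that any reported result is wrong.

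**What to change.** 1. State the between-arm analysis of the fitness scores: which scores, whether legs are combined, and whether the MANUAL test is an outcome. Use randomised arm as the factor.
2. Control family-wise error at 0.05 across the scores analysed, by one of two routes: Holm or a correlation-aware adjustment over the separate tests; or one multivariate test by arm followed by multiplicity-adjusted single-score tests. The multivariate test alone does not protect the single-score tests once any one score truly differs.
3. Use a single primary outcome at 0.05 only if that choice is documented as made before the data were seen. The document is dated May 2020, and injury follow-up ended in February 2018.
4. Report any score outside the controlled family as an estimate with a confidence interval, labelled exploratory.
5. Report injuries as a separate question at its own 0.05, and disclose that the two families together carry up to 10% false-positive risk.
6. Describe the 80% power as applying to one test at 0.05.

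The change affects analysis and reporting only. The price is less favourable p-values for some scores and the loss of single-score power shown in the working; a correlation-aware threshold recovers part of that loss.
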